6.1 Primary outcome

The primary analysis will compare the improvement in DSAP-GASI scores before treatment and after treatment in both groups. Only participants with clearly documented photos across all visits will be considered for the DSAP-GASI efficacy analysis. The scores will be graded by two blinded, trained physicians. Cronbach's Interrater reliability will be calculated among raters across visits and the scores will be averaged for each of the four visits. Overall efficacy will be examined using a 2X4 (Drug X Time) Repeated Measures Analyses of Variance (ANOVA). The statin/cholesterol vs statin groups will be compared and evaluated for significant differences

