5.1 Populations

Intention-to-treat (ITT)

All randomized study subjects.

Per Protocol (PP)

All randomized study subjects completing the whole study period (complete cases). For a specific analysis, study subjects with missing data on any of the variables in the model will be excluded from the analysis. Analyses of this population is seen as a sensitivity analysis to investigate whether conclusions are sensitive to assumptions regarding the pattern of missing data.

6. Analysis

All enrolled subjects are considered in the demographic data and safety analysis. Treatment efficacy is based on investigator-standardized patient-documented photographs. Repeat photo documentation will be obtained if image quality was inadequate or angle, lighting or location is not standardized to prior photos.

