6.2 Secondary Outcomes

Self-reported patient satisfaction on overall appearance, size, and color, will be recorded and examined using Chi-Square across drug for the final visit. Application frequency and safety may also be evaluated.

A cross-sectional analysis of sociodemographic data and self-reported DSAP-related impact on QoL (scale 1-10) was averaged at baseline, while the RAND36 and Dermatology Life Quality Index (DLQI) were distributed and averaged at weeks 0, 4, 8, and 12. Statistical measures used in analysis included a Repeated Measures Analyses of Variance (ANOVA) and Pearson correlation coefficient.

7. Missing Data

Patients who failed to submit photographs for the analysis will be removed from the DSAP-GASI efficacy analysis. Missing data will be recorded and excluded from analysis.

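### The SAP defines an ITT set and treats complete cases as a sensitivity set, yet its primary DSAP-GASI analysis is limited to patients with clear photos at every visit

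*SAP*

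**What the plan says.** SAP 5.1 defines two populations. ITT is every randomized subject. PP is "All randomized study subjects completing the whole study period (complete cases"), with the further rule "For a specific analysis, study subjects with missing data on any of the variables in the model will be excluded from the analysis". On the role of PP it says "Analyses of this population is seen as a sensitivity analysis to investigate whether conclusions are sensitive to assumptions regarding the pattern of missing data". It does not say which set is primary, but calling PP a sensitivity analysis implies that the main analysis uses something broader.

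SAP 6 assigns a population to two items: "All enrolled subjects are considered in the demographic data and safety analysis". It also has a retake rule: "Repeat photo documentation will be obtained if image quality was inadequate or angle, lighting or location is not standardized to prior photos".

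SAP 6.1 sets the primary efficacy population: "Only participants with clearly documented photos across all visits will be considered for the DSAP-GASI efficacy analysis". The model is given as "Overall efficacy will be examined using a 2X4 (Drug X Time) Repeated Measures Analyses of Variance (ANOVA"), with scores from four visits. SAP 7 adds "Patients who failed to submit photographs for the analysis will be removed from the DSAP-GASI efficacy analysis" and excludes missing data in general. SAP 6.2 names no population for the secondary outcomes. ITT is not mentioned after 5.1, and the protocol defines no analysis set.

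SAP 4.1 states the primary outcome at 12 weeks. SAP 2.1 gives 31 enrolled against a goal of 50.

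**The concern.** The population sections and the analysis sections do not fit together. If complete cases are the sensitivity set, the primary set should be wider, but 6.1 makes it just as narrow. This has two consequences.

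First, the sensitivity analysis cannot do the job that 5.1 gives it. Comparing one complete-case set with another that holds almost the same patients says little about how the result depends on missing data.

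Second, the rule would drop randomized patients who have usable data. That costs precision in a small trial. It can also bias the arm comparison if photo loss is linked to outcome differently in the two arms.

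**Working it through.** **Comparing the sets.** The documents state no power or loss figure to reproduce, so the first check is textual.

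| Place | Set | Use |
|---|---|---|
| SAP 5.1 | ITT: all randomized | None named |
| SAP 5.1 | PP: completers with no missing model variable | Sensitivity |
| SAP 6 | All enrolled | Demographics, safety |
| SAP 6.1 | Clear photos at all visits | Primary DSAP-GASI |
| SAP 6.2 | Not named | Secondary outcomes |
| SAP 7 | Those who failed to submit photographs removed | DSAP-GASI |

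In the 2x4 model the variables are arm, visit and score, so PP requires a score at all four visits. The 6.1 set requires a clear photo at all four. The two can differ at most by completers whose photos can be graded but are not judged clear.

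**How many patients the rule could drop.** Inputs: 31 patients (SAP 2.1; assumed all randomized) and three visits after baseline (schedule of events). The loss rate *m* per later visit is an assumption, and the baseline photo is taken as secured. Write p = 1 - m.

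- Independent losses: remaining = 31p³. Dropped only for week 4 or 8 = 31p(1 - p²). At m = 0.10 these are 31 × 0.729 = 22.6 and 31 × 0.9 × 0.19 = 5.3.
- Losses clustered within patients (beta-binomial, correlation 0.5): remaining = 31p(p+1)(p+2)/6. Dropped only for week 4 or 8 = 31[p - p(p+1)(p+2)/6]. At m = 0.10 these are 31 × 0.8265 = 25.6 and 31 × 0.0735 = 2.3.

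| Loss per visit | 2% | 5% | 10% | 15% |
|---|---|---|---|---|
| Remaining, independent | 29.2 | 26.6 | 22.6 | 19.0 |
| Remaining, clustered | 29.9 | 28.2 | 25.6 | 23.2 |
| Dropped only for week 4 or 8, independent | 1.2 | 2.9 | 5.3 | 7.3 |
| Dropped only for week 4 or 8, clustered | 0.5 | 1.2 | 2.3 | 3.2 |

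**Precision.** In simulation with independent loss at 5, 10 and 15%, the variance of the arm difference in change to week 12 was 1.11-1.17, 1.28-1.36 and 1.48-1.54 times as large with complete cases as with an unstructured mixed model. The ranges cover compound-symmetry and AR(1) correlations.

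**Bias.** Assumptions: no true arm difference; monotone loss that depends on outcome in one arm only; logistic slopes of 0.5, 1 and 2 per SD of the driver. Bias is in SDs of a single score, because SAP 4.1 does not say how the component grades are combined.

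| Loss follows | Complete cases, 66% complete | Mixed model, 66% complete | Complete cases, 90% complete |
|---|---|---|---|
| Last score | 0.02-0.10 | 0.005 or less | at most about 0.03 |
| Last observed change | 0.05-0.29 | 0.003 or less | at most about 0.10 |
| Change not yet seen | 0.10-0.42 | 0.06-0.27 | at most about 0.15 |

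Under independent equal loss, 66% complete corresponds to 1 - 0.66^(1/3) = 13% loss per visit, and 90% to 1 - 0.90^(1/3) = 3.5%. For scale, the standard error of the arm difference with about 20 completers is 0.40-0.45 SD.

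**The case against.** A conventional repeated-measures ANOVA needs a score at every visit, so 6.1 is consistent with its own model. The retake rule should reduce loss, the graders are blinded, and SAP 4.1 calls the measure exploratory. The links from photo loss to arm are weak: both arms receive lovastatin, and Protocol 13.0 anticipates no complications beyond minor local irritation. The gain from a mixed model is also uneven. At 66% complete with the two steeper slopes, false-positive rates at a nominal 5% were 4.7-5.4%, 5.5-9.4% and 7.6-12.2% for complete cases across the three mechanisms, against 5.0-5.7%, 5.1-6.0% and 6.4-8.3% for the mixed model. On that measure there is nothing to gain in the first case, and the third is only partly corrected.

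Much of this stands, and it limits the size of the point. It does not remove the conflict. The ANOVA's need for complete data is a property of the chosen method, and a mixed model fits the same drug and visit terms without it. The retake rule addresses image quality and framing. It does not guarantee a photo after withdrawal for an adverse event (Protocol 12.0) or when none is sent (SAP 7). Protocol 11.0 deletes emailed photos that miss its criteria and promises no replacement there.

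A reader might infer three stronger points that the documents do not support:

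- *That SAP 7 also demands clear photos at all four visits.* It mentions neither clarity nor the number of visits. That rule is in 6.1 alone.
- *That no secondary analysis uses ITT.* SAP 6.2 is silent, so the accurate statement is that none is assigned to it.
- *That unmasked staff select the photos.* The SAP does not say who judges clarity. This is a gap, not evidence of misuse.

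**Conclusion.** The inconsistency is real and concerns the primary analysis, so it should be fixed. The SAP reserves complete cases for sensitivity, then uses nearly the same set as primary, and leaves ITT without an efficacy analysis. The restriction is explicit for the primary outcome; for the secondary outcomes the population is simply unstated.

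The practical size is unknown because no loss rate is given. Near 2% loss per visit the rule costs one or two patients. At 10-15% it could leave roughly 19 to 26 of 31, depending on clustering. Bias needs outcome-related loss that differs by arm. In the one-arm illustration it is small at 90% complete and reaches a few tenths of an SD only at 66% complete. One might conclude that the trial's result is biased or that patients were discarded. The documents show only a rule that could have that effect.

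**What to change.** Replace the exclusion in SAP 6.1 and 7. The primary DSAP-GASI analysis should be by randomized arm, include every randomized subject with at least one gradable photo, and use all gradable photos in a likelihood-based mixed model for repeated measures. The terms are drug, visit and drug-by-visit, with unstructured covariance, small-sample degrees of freedom (such as Kenward-Roger) and a pre-specified fallback. The primary contrast is the drug difference in change from baseline to week 12. The fallback should use small-sample-corrected robust standard errors: compound symmetry with model-based errors gave 11-12% type I error under AR(1) correlation of 0.7-0.8.

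Alongside this:

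- Amend 5.1 to define this set as the primary efficacy set. It is narrower than the ITT set there, so state how randomized subjects with no gradable photo are counted and reported.
- Keep the all-four-photos set as the sensitivity analysis, and name the population for each analysis in 6.2.
- Have the blinded graders decide whether a photo is gradable.
- Report missing or ungradable photos by arm and visit, with reasons.
- Label the change post hoc if scores have already been analysed by arm.

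The cost is SAP wording, a few lines of code and some grading, with no new patients or visits. Extra photos per grader are 31(1 + 3p) - 4 × 31p³, or about 5, 13, 24 and 34 at 2, 5, 10 and 15% independent loss, if incomplete patients would otherwise go ungraded. The model relies on missing at random, so bias from loss driven by unseen outcomes is reduced, not removed. Subjects with only a baseline photo add almost nothing to the contrast.

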2.1 Sample Size Calculation

DSAP is a rare disease that effects people from a wide geographical region. The goal sample size for the study was to recruit 50 subjects, however, due to recruiting limitations and state regulations, we were only able to enroll 31 patients. No formal sample size calculation was necessary as this study is first of its kind.

3. Aims and Objectives

• The purpose of this study is to evaluate the effectiveness of cholesterol/lovastatin versus lovastatin alone to treat porokeratosis. Our working hypothesis is that both topical cholesterol/lovastatin and lovastatin alone are helpful in treating patients with disseminated superficial actinic porokeratosis (DSAP).

DSAP: Single-Blinded randomized trial

Aims:

- 1. To evaluate the response (lesion size, color, patient quality of life) to treatment with topical cholesterol/lovastatin and lovastatin alone in a series of patients with the diagnosis of DSAP.
- 2. To characterize lesion patterns following topical treatment and patterns of lesion regression.
- 3. Access quality of life outcomes through RAND36 and DLQI surveys.

4. Outcomes

This section will present the outcomes investigated to answer the study aims and objectives. The analyses are described in section 6 Analyses.

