4.1 Primary outcome

Percentage of lesion clearance after 12 weeks of therapy using an exploratory clinical measure modified from a validated psoriasis index. The Disseminated Actinic Porokeratosis General Assessment Severity Index (DSAP-GASI) included plaque/rim elevation, scaling, and color (0= clear, 1=almost clear, 2=mild, 3=moderate, and 4=severe).

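### Cronbach's coefficient measures consistency between the two raters, not agreement, so it can overstate agreement on the newly adapted DSAP-GASI

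*SAP*

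**What the plan says.** SAP 4.1 defines the primary measure as an "exploratory clinical measure modified from a validated psoriasis index". It covers rim elevation, scaling and color, on labelled grades: "0= clear, 1=almost clear, 2=mild, 3=moderate, and 4=severe".

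SAP 6.1 then says: "The scores will be graded by two blinded, trained physicians". Next, it says that Cronbach's "Interrater reliability will be calculated among raters across visits and the scores will be averaged", with one average at each of the four visits. The averaged scores go into a Drug by Time repeated measures ANOVA with two groups and four visits.

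SAP 6.1 also limits who enters: "Only participants with clearly documented photos across all visits will be considered for the DSAP-GASI efficacy analysis". The number of such participants is not given. SAP 2.1 puts a ceiling on it: "we were only able to enroll 31 patients".

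Neither document names an agreement ICC, a kappa, a mean rater difference, a reliability threshold or a rule for discordant grades. The SAP does not use the word alpha, but Cronbach's alpha is the only natural reading.

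**The concern.** The psoriasis index may be validated, but that does not carry over automatically to a modified score for another disease graded from photographs. The rater coefficient is therefore the only evidence on measurement quality that the plan will produce for its primary scale.

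The grades are named severity states and the primary outcome is expressed as clearance. Whether two physicians both call a lesion clear, or one calls it clear and the other almost clear, is a question of absolute agreement. Alpha answers a different one: whether the raters rank the photographs in the same way. A high alpha could be read as showing that the severity levels are reproducible when one rater grades consistently higher than the other.

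The phrase about visits adds a second difficulty. It could mean one coefficient pooled over four visits or one at each visit. Pooling puts any time trend in severity into the between-photograph variance, and so raises the coefficient. Neither reading gives the reliability of change, although SAP 6.1 says the primary analysis concerns improvement.

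**Working it through.** The documents state no reliability value, threshold or standard deviation, so there is no planned figure to reproduce. The check is algebra plus an illustration.

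**Formulas for two raters.** Vs is the true variance between photographs, Ve the rater error variance, and Vr = b²/2 the rater variance from a constant offset of b grades.

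- Alpha = two-rater consistency ICC = Vs / (Vs + Ve/2)
- Two-rater agreement ICC = Vs / (Vs + (Vr + Ve)/2)
- Single-rater agreement ICC = Vs / (Vs + Vr + Ve)

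Vr is absent from alpha. That holds whatever the standard deviations are.

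**Small example.** Rater 1 gives 1, 2, 3, 0, 2, 1 and rater 2 is always one grade higher. The residual mean square is 0, the subject mean square 2.2 and the rater mean square 3. Alpha is 1.00. The two-rater agreement ICC is 2.2 / (2.2 + 3/6) = 0.81, and the single-rater value is 2.2 / (2.2 + 2 × 3/6) = 0.69.

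**Illustration; every input is an assumption.** Patient SD 0.7, visit-level SD 0.35, rater error SD 0.4, mean fall of 0.5 grade per visit, no truncation at 0 or 4.

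- One visit: Vs = 0.49 + 0.1225 = 0.6125; Ve = 0.16.
- Pooled: visit means of 0, 0.5, 1 and 1.5 below baseline have variance 0.3125, so Vs = 0.6125 + 0.3125 = 0.925.
- Alpha, one visit: 0.6125 / (0.6125 + 0.08) = 0.88. Alpha, pooled: 0.925 / (0.925 + 0.08) = 0.92.
- Two-rater agreement ICC, pooled, offset 1: Vr = 0.5, so 0.925 / (0.925 + 0.33) = 0.74.

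Means from simulation with 31 patients, with the closed-form value in brackets where it differs:

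| Offset (grades) | Pooled alpha | Pooled two-rater agreement ICC | One-visit alpha | One-visit two-rater agreement ICC |
|---|---|---|---|---|
| 0 | 0.92 | 0.92 | 0.88 | 0.88 |
| 0.5 | 0.92 | 0.86 (0.87) | 0.88 | 0.80 (0.81) |
| 1 | 0.92 | 0.73 (0.74) | 0.88 | 0.64 (0.65) |

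On these inputs, pooling moves alpha from 0.88 to 0.92.

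**Change from week 0 to week 12.** True variance of change is 2 × 0.1225 = 0.245, and the error variance of the two-rater mean change is 2 × 0.16 / 2 = 0.16. Reliability is 0.245 / 0.405 = 0.60 in closed form and about 0.58 in simulation, at any offset.

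**Other assumptions.** With patient SD 0.8 and rater error SD 0.6, one-visit alpha is 0.78 at any offset, and the two-rater agreement ICC is 0.78, 0.73 and 0.60 at offsets of 0, 0.5 and 1. Adding a visit-level SD of 0.3 and a total fall of 1 grade gives, in simulation, a pooled alpha of about 0.82 and a reliability of change of about 0.29.

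**The case against.** The strongest reply is that nothing in the analysis depends on this coefficient. SAP 6.1 sets no threshold, and the analysis uses the mean of two raters. If both score every photograph, a constant offset shifts every averaged score by the same amount and cancels from the Drug, Time and Drug by Time contrasts. This stands, and it limits the point to reporting and to the reading of absolute grades.

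Further replies stand in part:

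- A reader might infer that alpha will overstate agreement here. The documents do not support that. Without an offset, alpha equals the two-rater agreement ICC, and the documents contain no rater data. Nothing suggests a full-grade offset between two trained physicians.
- A reader might take pooling as settled. The wording allows one coefficient per visit just as well. Pooling raises alpha only if mean severity changes, although the working hypothesis expects that it will.
- A reader might set alpha against the single-rater ICC and report a larger gap. That is not like for like, because the two-rater mean is analysed.
- A reader might fear bias at visits graded by one rater. No such visit is planned.
- Grades stop at 0 and 4, so an offset cannot be exactly constant and alpha would move somewhat. With an assumed baseline mean of 3 and truncation, pooled alpha at a 1-grade offset falls from 0.92 to 0.89. It still does not report the offset.

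**Conclusion.** The point holds as a limited one about the choice of reliability statistic. That alpha cannot register a constant rater difference is algebra and needs no assumption. How much it overstates agreement depends on an offset that the documents do not report: nothing at zero offset, 0.06 at half a grade and 0.19 at a full grade, for the pooled two-rater figures under the assumed standard deviations. The gap between pooled alpha and the reliability of change (0.92 against about 0.58) exists without any offset, but it too depends on the assumed variances.

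What is affected is the reliability reported for a new scale and the interpretation of absolute severity or clearance levels. A reader might infer that the arm comparison is biased; the documents do not support this as long as both raters score every photograph, as SAP 6.1 implies by averaging their scores. This is a worthwhile improvement, not a threat to the primary result.

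**What to change.** In SAP 6.1, replace the sentence on Cronbach's coefficient with wording such as: *Agreement between the two raters will be reported as the two-way random-effects absolute-agreement ICC with 95% CI, separately at each visit and for change from baseline. The ICC for the two-rater mean is the main figure, because that mean is analysed; the single-rater ICC is supplementary. The mean difference between raters will also be reported.* A weighted kappa for each component grade is optional.

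This also removes the ambiguity about visits. It needs no further rater and no new grading, only the two raters' separate scores, which alpha would need as well. The cost is one sentence and a less flattering result: the coefficient will probably be lower and, with 31 patients or fewer, its interval wide.

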6.2 Secondary outcomes	
7. Missing data	

1 Introduction

The aim of this study is to test in a single-center randomized clinical trial, if topical statins combined with topical cholesterol can reduce the severity (size, color, quality of life impact) of disseminated superficial actinic vs statin therapy alone.

This statistical analysis plan (SAP) will give more detailed descriptions of the endpoints in the study and the corresponding analysis.

2 Study Design

Patients with previous diagnosis of DSAP will be approached for informed consent as directed in sections 8.0 and 9.0 of the protocol. If the patient is eligible for the study, he or she will be randomly assigned to one of two groups, Group A (cholesterol/lovastatin) and Group B (lovastatin only). The patient will not be informed of which group they are in and will not be informed of what their study medication is, allowing single-blinding. Researchers will not be masked.

Enrolled subjects will be followed up at monthly intervals for three months via virtual check-in using an MUSC approved HIPAA compliant technology. At each visit, participants will undergo brief, limited physical examination (in order to determine disease severity and affected body surface area); additionally, clinical photographs of the lesion will be obtained in clinic or shared virtually with the investigators via secure email (sent to MUSC Outlook email). The physical exam will occur in-person or by using the virtual visit technology, which allows us to see the patient and visualize their skin findings. Photographs will be stored in the coded study-specific medical record for further analysis of lesion features.

At each visit a Patient Quality of Life, Physician Global Assessment Scale, and RAND36 will be administered.

Patients will be contacted via formal virtual visits at weeks 4, 8, and 12 and non-formal check-ins at weeks 2 and 6. Patients will be asked about compliance and any adverse effects experienced. Patients are also encouraged to contact [name] and/or [name] at any given point during the study if they think they are experiencing study-related side effects. Immediate consultation will follow to determine the severity of such event and necessary impacts on patient health and participation. Non-formal check-ins will be done over phone by study team member to assess for any adverse effects at weeks 2 and 6 of treatment.

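### SAP 6.1 tests Drug x Time over four visits, but plans no week-12 between-arm estimate with a confidence interval and drops patients who have both photographs that such an estimate needs

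*SAP*

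**What the plan says.** The question is between arms. SAP section 1 asks whether adding topical cholesterol to a topical statin "can reduce the severity (size, color, quality of life impact) of disseminated superficial actinic vs statin therapy alone". SAP 4.1 sets the measure and the time point: "Percentage of lesion clearance after 12 weeks of therapy using an exploratory clinical measure". That measure, DSAP-GASI, "included plaque/rim elevation, scaling, and color" on a 0 to 4 severity scale.

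SAP 6.1 describes the analysis. It opens with "The primary analysis will compare the improvement in DSAP-GASI scores before treatment and after treatment in both groups". On scoring it says "The scores will be graded by two blinded, trained physicians", and the raters' scores are averaged at each of the four visits. Then: "Overall efficacy will be examined using a 2X4 (Drug X Time) Repeated Measures Analyses of Variance (ANOVA", and "The statin/cholesterol vs statin groups will be compared and evaluated for significant differences". The visits are weeks 0, 4, 8 and 12, so baseline is one of the four outcome levels and not a covariate.

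On who is analysed, SAP 6.1 says "Only participants with clearly documented photos across all visits will be considered for the DSAP-GASI efficacy analysis", and SAP 7 removes patients who did not send photographs. SAP 5.1 defines an ITT set of all randomised subjects and treats complete cases as a sensitivity analysis.

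Protocol 11.0 plans descriptive statistics for continuous data, including means and standard deviations, without saying that they are by arm. Its only named test is a within-patient paired t-test. The one between-arm test tied to the final visit is a chi-square on self-reported outcomes (SAP 6.2). Neither document states an alpha, a week-12 between-arm contrast for DSAP-GASI, or a confidence interval.

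**The concern.** The aim and the outcome together call for one quantity: how much DSAP-GASI differs between the arms at week 12, and how precisely that is known. The 2x4 ANOVA does not supply it.

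- **Drug x Time** asks whether the difference between arms changes anywhere across four visits. It has 3 degrees of freedom and no direction or size.
- **Drug** averages baseline, where randomised arms differ only by chance, with weeks 4, 8 and 12. It estimates only a fraction of the week-12 difference.
- **Time** can be significant when the arms do not differ at all.

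With at most 31 patients (SAP 2.1), a p-value without an interval says little, above all if it is not significant. The photograph rule then removes patients who have everything a week-12 comparison needs, because a four-level ANOVA needs all four visits.

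**Working it through.** The plan gives no power, alpha, effect size, SD or correlation, so there is no figure to reproduce. What follows is an illustration.

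**From the documents:** 31 enrolled (SAP 2.1), 1:1 allocation (protocol 10.0), four visits.

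**Assumed:** arms of 15 and 16; two-sided 0.05; normal scores with unit SD; equal correlation r between visits of 0.3, 0.5 or 0.7; week-12 difference of 1 SD. Thirty-one is a ceiling, because only complete-photograph cases enter the analysis.

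**Formulas.** Let h = 15 x 16 / 31 = 7.74, and let d be the arm difference at weeks 0, 4, 8 and 12, with mean m and S = sum of (d - m)². Power comes from the noncentral F with noncentrality L.

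- Drug x Time: L = h S / (1 - r), df 3 and 87
- Drug: L = h m² / ((1 + 3r)/4), df 1 and 29
- Unadjusted week-12 change: L = h / (2(1 - r)), df 1 and 29
- Week 12 adjusted for baseline (ANCOVA): L = h / ((1 - r²)(1 + 1/27)), df 1 and 28. The factor 1 + 1/27 allows for chance baseline imbalance.

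**Profiles.** Linear (0, 1/3, 2/3, 1): m = 0.50, S = 0.556. Early step (0, 1, 1, 1): m = 0.75, S = 0.75. Late step (0, 0, 0, 1): m = 0.25, S = 0.75. Weeks 4 and 8 only (0, 1, 1, 0): S = 1.00.

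| Test | L at r = 0.3/0.5/0.7 | Power, % |
|---|---|---|
| Drug x Time, linear | 6.14 / 8.60 / 14.34 | 51 / 67 / 89 |
| Drug x Time, early or late step | 8.29 / 11.61 / 19.35 | 65 / 81 / 96 |
| Unadjusted week-12 change | 5.53 / 7.74 / 12.90 | 62 / 77 / 93 |
| ANCOVA at week 12 | 8.20 / 9.95 / 14.64 | 79 / 86 / 96 |

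The ANCOVA gain over Drug x Time is therefore 28/19/7 points for linear divergence and about 14/5/0 for a step.

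For the Drug term, m shows that it estimates 0.50 (linear), 0.75 (early step) or 0.25 (late step) of the week-12 difference. Its power is about 50/40/33% for the linear profile.

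If the arms differ by 1 SD at weeks 4 and 8 but not at week 12, Drug x Time has L = 11.06/15.48/25.81 and is significant in 79/91/99% of trials.

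**95% CI half-width at week 12, in SD:**

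- Unadjusted change: 2.045 x sqrt(2(1 - r)/7.74) = 0.87 / 0.74 / 0.57
- ANCOVA: 2.048 x sqrt((1 - r²)(28/27)/7.74) = 0.72 / 0.65 / 0.54

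**Smaller effect.** With a 0.5 SD difference, ANCOVA power is only about 28/33/45%.

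**Photograph rule.** Suppose baseline is always present and each later photograph is independently missing with probability p. Requiring all visits keeps 31(1 - p)³ patients; requiring baseline and week 12 keeps 31(1 - p). For assumed p of 5/10/20% that is 26.6/22.6/15.9 against 29.5/27.9/24.8.

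**The case against.** Much of the defence stands.

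- SAP 6.1 does commit to comparing the arms. Its reference to improvement from before to after treatment most naturally means Drug x Time, which is a valid test. A reader might infer that no between-arm analysis is planned, or that the diluted Drug term decides. The text supports neither.
- A reader might infer that no estimate will exist at all. Protocol 11.0 plans means and SDs. If these were tabulated by arm and visit, an unadjusted week-12 difference and interval could be worked out by hand. What is missing is a planned inferential estimate.
- A reader might infer a doubled error rate, since 1 - 0.95² = 9.75% if a significant Drug or Drug x Time term would each count. The SAP does not say that either would do.
- A reader might infer biased scoring, because the researchers are not masked. DSAP-GASI is graded by two blinded physicians, so the issue here is the test and not the grading.
- Linear divergence flatters the alternative. Protocol 2.0 cites clearance after 4 weeks in a previous series, so an early step is at least as plausible, although that says nothing about the difference between arms. Under either step, Drug x Time beats the unadjusted week-12 change contrast (65/81/96% against 62/77/93%). For an early step at correlation 0.3, even the Drug term beats ANCOVA (83% against 79%).
- SAP section 6 provides for repeat photographs when quality or angle is inadequate. That reduces unusable images but does not cover photographs that are never sent.

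The SAP also calls the measure exploratory and makes no sample size claim. That weakens any argument from power, but not the need for an interval: the SAP labels this analysis primary.

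**Conclusion.** The point holds as a matter of estimation and efficiency, not validity. The plan answers a week-12 between-arm question with an omnibus test over four visits, reports no inferential week-12 difference, and excludes patients who lack only an intermediate photograph. That is worth correcting before the result is reported.

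Its size depends on inputs that the documents do not give. Under the stated assumptions the power gain from a baseline-adjusted week-12 comparison runs from about 28 points to none, so a claim that it always wins on power would go too far. Its interval is narrower than that of the unadjusted change throughout: the unadjusted one is wider by about 22/13/6%. The real score is built from bounded 0 to 4 grades, so the normal model is only approximate. How many patients the photograph rule costs is unknown.

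The rule for combining the three components, the percentage-clearance formula and the role of the paired t-test are separate questions and are not settled here.

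**What to change.** In SAP 6.1, make the primary between-arm result the week-12 difference in DSAP-GASI, adjusted for baseline DSAP-GASI by ANCOVA, with a 95% CI and two-sided alpha 0.05. Include every randomised patient, in the assigned arm, who has gradable baseline and week-12 photographs. Align SAP 7 with this and report exclusions by arm. Keep the 2x4 ANOVA as a supportive analysis, and name Drug x Time as its between-arm term.

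Date the change and state what outcome data had been seen by then. SAP 2.1 already reports final enrolment, and protocol 13.0 has available efficacy data compiled every other month.

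The cost is wording only; no new data are needed. There are two downsides. A difference confined to weeks 4 and 8 would show only in the supportive analysis. Patients without a week-12 photograph stay excluded, so the result is still not the full ITT set of SAP 5.1.

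A smaller edit would keep the ANOVA as primary, name Drug x Time as the deciding term, and add an unadjusted week-12 change contrast with its CI. That also supplies the missing estimate, with the wider interval shown above, but by itself leaves the photograph rule unchanged.
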